1 PROTOCOL SUMMARY

1.1 SYNOPSIS	
Title:	A Single Arm Study of Resting State Functional Magnetic Resonance Imaging (rs- fMRI)-Guided Theta Burst Stimulation (TBS) in Early-Stage Alzheimer's Disease (AD)
IRB Number:	
Study Description: Objectives:	Alzheimer's disease (AD) is a progressive neurodegenerative condition affecting 6.2 million individuals in the United States, resulting in an annual cost of care of \$305 billion. AD is functionally characterized by progressive degeneration of large-scale brain networks (LSBNs), including the default mode network (DMN) presumably from the deposition of amyloid plaques and neurofibrillary tangles. Available FDA-approved medications for AD such as donepezil and memantine offer limited benefit and modest impact on quality of life. In combination with resting state functional MRI (rs-fMRI), transcranial magnetic stimulation (TMS) with intermittent theta burst stimulation (iTBS) offers a non-invasive alternative to pharmacotherapy in persons with AD. We propose a pilot trial using rs-fMRI to target dysfunctional LSBNs in early stage AD. Primary Aim : To estimate the effect of rs-fMRI-guided TBS on connectivity dysfunction within the temporal area G dorsal (TGd) in persons with early stage AD.
	Exploratory Aim 1: To estimate the effect of rs-fMRI-guided TBS on the Repeatable Battery for the Assessment of Neuropsychological Status (RBANS) score in persons with early stage AD.
	Exploratory Aim 2: To estimate the effect of rs-fMRI-guided TBS on the Geriatric Depression Score (GDS) in persons with early stage AD.
	Exploratory Aim 3: To identify and estimate the effect of rs-fMRI-guided TBS on two additional dysfunctional parcellations within the default modal network (DMN), central executive network (CEN), and salience network (SN) in persons with early stage AD.
Endpoints:	 Primary Endpoint: Connectivity Measures of the TGd parcellations at baseline and post-treatment Exploratory Endpoints: RBANS at baseline and post-treatment GDS at baseline and post-treatment Connectivity levels of other parcellations that are anomalous
 Connectivity levels of other parcellations that are anomalous Study Population: The study will enroll 10 subjects with a diagnosis of early stage AD (mild cognitive impairment or mild AD). Inclusion criteria: Established diagnosis of MCI/mild AD Evidence for CNS amyloidosis (e.g., Amyloid PET or CSF biomarkers consistent with AD) Prior brain imaging performed MMSE >24 CDR 0.5-1 	

	Stable dose of cholinesterase inhibitors and memantine for at least one month			
	7. Subjects are between 40-90 years of age			
	Exclusion Criteria:			
	 Non-AD dementia including, but not limited to, Lewy body dementia, frontotemporal dementia, vascular dementia, Jakob-Creutzfeldt disease, etc. 			
	2. Inability to tolerate rs-fMRI			
	3. Contraindication of rs-fMRI due to implants or metal			
	4. Seizure disorder			
	5. Alcoholism			
Description of Sites/Facilities	Participants will be enrolled at HealthPartners Neuroscience Center,			
Enrolling	located at [name].			
Participants:				
Description of	All subjects will receive treatment with intermittent theta burst stimulation			
Study	(iTBS), There will be a total of 5 iTBS sessions per treatment visit, and a total of			
Intervention:	5 treatment visits distributed over a two-week period (#3 during week 1 and #2 during week 2). All patients will receive iTBS to the right TGd region. In addition, we will further provide TBS treatment for two additional sites within the LSBNs that is found to contain the greatest number of connectivity anomalies. Data from the Infinitome program will be exported to the Localite TMS Navigator; the navigator is a device that visualizes brain regions to facilitate correct positioning of patient and coil based on the coordinates from the Infinitome			
Study Duration:	the Infinitome analysis.			
Study Duration.	The duration of this study is 1.5 years.			
Participant Duration:	10-12 weeks			

1.2 SCHEMA

[figure not shown]

Figure 1: Study Visit/Workflow

1.3 SCHEDULE OF ACTIVITIES (SOA)

Table 1: Study Visit Schedule

Procedure	Screening	Baseline	Treatment	Follow-up	Early Withdrawal
Visit #	Visit 1	Visit 2	Visits 3-7	Visit 8	
	Day 0	Week 1	Weeks 2-4	Week 10	
Window		\pm 7 Days	\pm 7 Days	\pm 7 Days	
Informed consent	Х				
Medical History	Х				
Demographics	Х				
MRI Contraindications	х	х	Х		
Concomitant Medications	Х	Х	х	x	x
Inclusion/Exclusion Criteria	х	Х	х		
MMSE	Х				
CDR	Х				
TMS Safety Questionnaire	Х	Х			
Physical Exam	Х				Х
RBANS		Х		Х	
GDS		Х		Х	
iTBS Treatment			Х		
MRI Imaging		Х		Х	
Adverse Events/Serious Adverse Events	Х	Х	Х	Х	x

2 INTRODUCTION

2.1 STUDY RATIONALE AND BACKGROUND

Alzheimer's disease is the most common cause of dementia, the 6th leading cause of death, and the only illness among the top ten that cannot be slowed, prevented, or cured (cite All Association Facts and Figures). The condition affects 6.2 million Americans and results in \$305 billion in annual costs ("2021 Alzheimer's disease facts and figures," 2021). The pathological signature of AD is the presence of cerebral amyloid plaques and neurofibrillary tangles resulting

in disrupted connectivity of large-scale brain networks (LSBN), including, but not limited to the default mode network (DMN). Available FDA approved treatments for AD temporary alleviate symptoms but have no bearing on overall disease progression (Mielke et al., 2012). Furthermore, cholinesterase inhibitors, the most commonly prescribed drugs for AD, cause dose-limiting gastrointestinal side effects in 20% of patients. Therefore, the current limitations of cognitively enhancing medications suggest a role for a more targeted treatment in AD.

Transcranial magnetic stimulation (TMS) is a therapeutic tool, consisting of magnet and coil that utilizes Faraday's principle to induce electric currents in specific brain regions, leading to cortical excitability or suppression (Janicak & Dokucu, 2015). The treatment is relatively safe with the most common side effect being tension headache (to which patients frequently acclimate over time) and is FDA-approved for the treatment of depression (Janicak & Dokucu, 2015). The device is routinely used in outpatient psychiatry clinics including HealthPartners and Park Nicollet behavioral health. Repetitive TMS (rTMS) has been shown to induce changes in cortical excitability and modulate neural network activity beyond the duration of the stimulus itself (Pascual-Leone et al., 2011). Intermittent theta burst stimulation (iTBS) is a more recent variation of TMS that delivers longer lasting change in brain activity with less stimulation and has likewise been found to be safe and well-tolerated by patients (Blumberger et al., 2018; Gonsalvez, Baror, Fried, Santarnecchi, & Pascual-Leone, 2017). Whereas, rTMS applied to the dorsolateral prefrontal cortex is an FDA approved treatment for refractory depression, TMS has significant potential as a targeted treatment for cognitive disorders. A proposed mechanism is that persistent enhancement of cortical excitability results in long-term potentiation (Huang, Edwards, Rounis, Bhatia, & Rothwell, 2005) and increased expression of brain derived neurotrophic factors (Phillips et al., 1991).

In addition to improving mood, TMS has demonstrated positive effects on cognitive performance. TMS has been shown to improve memory in young and healthy elderly individuals (Manenti, Cotelli, Robertson, & Miniussi, 2012) as well as in memory impaired adults (Gonsalvez et al., 2017). In mild-moderate AD, rTMS at 20 Hz applied over the DLPFC resulted in improvement of object naming at 8 weeks (Cotelli et al., 2011). In addition, this frequency and anatomical location has improved performance in mild AD on the MMSE, the instrumental activities of daily living (IADL) scales, and global deterioration scale at 3 months, but no such benefits were noted in severe stage dementia (Ahmed, Darwish, Khedr, El Serogy, & Ali, 2012). An investigation targeting the precuneus, a hub within the DMN, with 20 Hz stimulation lead to improved episodic memory performance compared to sham (Koch et al., 2018). In addition, this study was remarkable in showing that iTBS, a more efficient approach to non-invasive neurostimulation, was well-tolerated in prodromal AD (Koch et al., 2018) In addition to AD, rTMS applied to the DLPFC at 10 Hz in MCI has resulted in cognitive benefits (Marra et al., 2015). The use of rTMS in conjunction with concurrent cognitive training has further improved

outcomes relative to placebo on the ADAS-Cog, MMSE, and CGIC lasting up to 4.5 months (Bentwich et al., 2011; Lee, Choi, Oh, Sohn, & Lee, 2016; Jose Martin Rabey & Dobronevsky, 2016; Jose M Rabey et al., 2013). Prior areas that have been targeted by TMS treatments for memory impairment in AD include the left/right dorsal prefrontal cortex, left inferior frontal gyrus, left middle temporal gyrus, left/right temporal parietal junction, precuneus, and left/right superior parietal lobule (Gonsalvez et al., 2017).

Investigation of the role of TMS in AD has been guided by anatomical landmarks, prolonged EEG, and structural imaging, but has yet to leverage resting state fMRI (rs-fMRI) imaging of LSBNs. rs-fMRI clinical tool relies on the low-frequency fluctuation in the blood-oxygen-level-dependent contrast (BOLD) signal to interrogate LSBNs (Joo, Lim, & Lee, 2016). In the behavioral health literature, rs-fMRI has been employed to better target key brain regions and networks responsible for mood regulation and have shown improvements in mood compared to standard approaches to treatment (Cole et al., 2019). Thus, the combination of rs-fMRI with TMS has the potential to enhance outcomes in targeted interventions for cognitive dysfunction.

[figure not shown]
Omniscient (Forbes Startup - 30 Million), a for-profit, Sydney, Australia-based company, has designed the Infinitome program, which utilizes data from the Human Connectome Project (HCP) together with machine learning to analyze diffusion tensor and resting-state fMRI imaging data from remote sites. The HCP commenced one of the most ambitious neuroscientific initiatives to "map the brain(Glasser et al., 2016)," identified 379 functional areas of the cerebrum, and discovered 97 new brain regions that had not been previously described. The foundation for this imaging tool is based upon the HCP atlas, which has also informed prior publications from our group, including the Connectomic Atlas of the Human Cerebrum (Baker et al., 2018). The Infinitome program creates a subject specific version of the Human Connectome Project Multimodal Parcellation (HCP-MMP1) atlas using diffusion tractography (DT). Analytics are performed on both diffusion tensor imaging (DTI) and rs-fMRI (see appendix Guide to Planning an Infinitome Study). Outlier detection using a tangent space connectivity matrix is performed by comparing results with a subset of 300 normal HCP subject fMRI samples to determine the range of normal correlations for each regions of interest in a LSBN. Abnormal connectivity is determined as a 3-sigma outlier for that correlation. The program includes a 15-minute imaging protocol that can readily be added on to structural MRI sequences and provides automated support for image analysis, thus simplifying the process of accessing clinically applicable imaging data. Preliminary work has shown that connectomic analysis in AD subjects using this software is feasible and can detect functional anomalies involving regions of interest described by the HCP (Ren et al., 2020).

Our preliminary research at HealthPartners using Infinitome in AD (n=4) and dementia with Lewy bodies (n=6) has shown temporal area G dorsal (TGd) (**Figure 2**) within the default mode network to have connectivity anomalies in persons with dementia. We suspect this area to be

important in the clinical presentation of various dementia, and therefore, these regions may be targeted with transcranial magnetic stimulation to improve symptoms.

Figure 2: Temporal Area Gd

2.2 RISK/BENEFIT ASSESSMENT

2.2.1 KNOWN POTENTIAL RISKS

Transcranial Magnetic Stimulation (TMS)

The TMS device to be used in this study is the MagVenture TMS Therapy[®] with theta Burst stimulation. MagVenture is a computerized, electromechanical medical device that produces and delivers non-invasive, magnetic fields to induce electrical currents targeting specific regions of the brain. In 2018, MagVenture received FDA clearance for the 3 minute protocol which we market under the trademarked name Express TMS[®]. The Lancet: "THREE-D: a randomized non-inferiority trial"), comparing the standard, 37 minute TMS protocol to the newer, 3 minute Theta Burst protocol (TBS) (Blumberger et al., 2018). The study concluded that the Theta Burst protocol is just as safe and effective for the treatment of major depressive disorder as standard TMS. Recent safety review of TMS summarizes the Theta Burst studies and concludes that TBS in the range of 80-100% of motor threshold is safe (Supplementary Table 5, (Rossi et al., 2020)). In this study, the planned motor threshold is 80%.

The TMS devices are non-significant risk devices, in line with the criteria for exception from an IDE. Transcranial magnetic stimulation (TMS) is a therapeutic tool, consisting of magnet and coil that utilizes Faraday's principle to induce electric currents in specific brain regions, leading to cortical excitability or suppression (Janicak & Dokucu, 2015) . The treatment is relatively safe with the most common side effect being tension headache (to which patients frequently acclimate over time) and is FDA-approved for the treatment of depression (Janicak & Dokucu, 2015). The device is routinely used in outpatient psychiatry clinics including HealthPartners and Park Nicollet behavioral health. Patients are generally able to drive home or return to work immediately after an TMS session. Rare side effects include dizziness, memory trouble, trouble concentrating and sudden mood changes. The long-term effects of TMS are not known.

Magnetic Resonance Imaging (MRI)

Structural MRI is a routine diagnostic procedure at HealthPartners, and the resting state portion merely requires 15 minutes of scan time. The patient may experience claustrophobia with the narrow imaging space and hearing loud noises while inside the machine. An MRI scan does not involve radiation like conventional X-rays. Instead, images are generated using a magnetic field and radio signals. Because an MRI scanner uses strong magnets, subjects will be screened by the NSC Imaging staff – as for a routine MRI. People with artificial heart valve, metal plate, pin, or other metallic objects in their body (including gun shot or shrapnel) will not be eligible for this study.

Neuropsychological Testing

Neuropsychological testing may result in frustration on the part of the patient but does not have any other significant risks.

Loss of Confidentiality

There may be a slight possibility of breach of confidential information that was collected. However, the following procedures will be implemented to reduce this risk:

- Data collection and reporting tools will be developed and stored internally.
- Data collected and stored electronically will remain confidential and secure (e.g. secured server and password protected files [REDCap]).
- Study binders will be stored in a locked file cabinet within a locked office.
- After the study is closed, all subject identifiers will be destroyed.

2.2.2 KNOWN POTENTIAL BENEFITS

Benefits for the patient include the ability to review imaging of their rs-fMRI imaging studies. In addition, patients may experience improvements in mood or cognition with the TMS although this has not been well-established at this time.

This research will be important to better investigate the role of non-invasive neurostimulation for symptoms in AD in a larger cohort and will support a future application for an NIH-sponsored grant.

2.2.3 ASSESSMENT OF POTENTIAL RISKS AND BENEFITS

We believe the potential risks to the participants in this study are minimal.

The following measures will be taken to protect patients from risk of TMS

 Transcranial magnetic stimulation is associated with a 50% risk of self-limiting headache and a 1/10,000 risk of seizures. All patients will undergo the TMS Adult Safety Screen (TASS), which will ensure that the risk of seizure is negligible for each subject participating in the study. In the event of adverse events during TMS treatment, specific procedures will be outlined (aligned with HealthPartners Behavioral Health) and staff will be trained and on-site for any assistance. In addition, all research staff will be

trained on the operation of device (Fried et al., 2020). Repeated exposure to TMS may result in sensorineural hearing loss, which is prevented by routine use of ear plugs.

• Relative to most oral medications used in treatment of dementia, TMS has a very favorable side effect profile.

The following measures will be taken to protect providers and patients from the risk of breach of confidentiality:

- A unique study ID code unrelated to the medical record number or other study subjectspecific information will be assigned to each patient and used to link data from various sources and needed for analysis. The study number will be used on the RedCap database and Infinitome Program. All imaging data uploaded from the NSC research site will be deidentified and uploaded to the Infinitome cloud-based server.
- Infinitome program uses an industrial grade cyber security that is superior to what is
 offered at the leading medical device companies. No personal health information is
 stored on servers and only de-identified scans are stored on a dedicated edge node on
 encrypted MinIO instances. Patient data is only accessed through authenticated calls
 form Kubernetes pods contained in the VPC. The web service requires user
 authentication. Only the data related to a specific facility can be retrieved through
 authenticated calls and are restricted to their use.

3 OBJECTIVES AND ENDPOINTS

OBJECTIVES	ENDPOINTS	JUSTIFICATION FOR ENDPOINTS
Primary		
To estimate the effect of rs-fMRI- guided TBS on connectivity dysfunction within the temporal area temporal area G dorsal (TGd) in persons with early stage AD.	Connectivity measures of the TGd parcellations at baseline and post- treatment	Infinitome processed rs- fMRI data that is targeted with TMS
Exploratory		
 To estimate the effect of rs- fMRI-guided TBS on the Repeatable Battery for the Assessment of Neuropsychological Status (RBANS) score in persons with early stage AD. To estimate the effect of rs- fMRI-guided TBS on the Geriatric Depression Score (GDS) in persons with early 	 RBANS at baseline and post- treatment GDS at baseline and post- treatment 	Provide pilot data for larger trials.

Table 2: Objectives and Endpoints

OBJECTIVES	ENDPOINTS	JUSTIFICATION FOR ENDPOINTS
3. To identify and estimate the effect of rs-fMRI-guided TBS on two additional dysfunctional parcellations within the default modal network (DMN), central executive network (CEN), and salience network (SN) in persons with early stage AD.	3. Connectivity levels of other parcellations that are anomalous	

4 STUDY DESIGN

4.1 OVERALL DESIGN

This investigation is a prospective single arm treatment trial in early stage AD (MCI and mild AD).

Primary Aim

To estimate the effect of rs-fMRI-guided TBS on connectivity dysfunction within the temporal area temporal area G dorsal (TGd) in persons with early stage AD.

Exploratory Aims

- 1. To estimate the effect of rs-fMRI-guided TBS on the Repeatable Battery for the Assessment of Neuropsychological Status (RBANS) score in persons with early stage AD.
- 2. To estimate the effect of rs-fMRI-guided TBS on the Geriatric Depression Score (GDS) in persons with early stage AD.
- **3.** To identify and estimate the effect of rs-fMRI-guided TBS on two additional dysfunctional parcellations within the default modal network (DMN), central executive network (CEN), and salience network (SN) in persons with early stage AD.

4.2 OVERVIEW – STUDY PROCEDURES/DATA COLLECTION

Early AD (MCI and Mild AD) patients will be recruited from a multidisciplinary dementia clinic. Patients will receive TMS treatment and data will be obtained for cognitive measures and imaging. This research investigation will take place at the Center for Memory and Aging at the HealthPartners Neuroscience Center (multidisciplinary dementia clinic).

4.3 END OF STUDY DEFINITION

A participant is considered to have completed the study if he or she has completed study visits and assessments.

5 STUDY POPULATION

The study will enroll 10 subjects with a diagnosis of early stage AD (mild cognitive impairment or mild AD). Those patients where fMRI is contraindicated (e.g. implantable device, pacemaker, metallic implants, etc.) or who are unable to tolerate sitting for a one-hour fMRI will be excluded from the study.

5.1 INCLUSION CRITERIA

In order to be eligible to participate in this study, an individual must meet all of the following criteria:

- 1. Established diagnosis of MCI/mild AD
- 2. Evidence for CNS amyloidosis (e.g., Amyloid PET or CSF biomarkers consistent with AD)
- 3. Prior brain imaging performed
- 4. MMSE >24
- 5. CDR 0.5-1
- 6. Stable dose of cholinesterase inhibitors and memantine for at least one month
- 7. Subjects are between 40-90 years of age

5.2 EXCLUSION CRITERIA

An individual who meets any of the following criteria will be excluded from participation in this study:

- 1. Non-AD dementia including, but not limited to, Lewy body dementia, frontotemporal dementia, vascular dementia, Jakob-Creutzfeldt disease, etc.
- 2. Inability to tolerate rs-fMRI
- 3. Contraindication of rs-fMRI due to implants or metal
- 4. Seizure disorder

5.3 LIFESTYLE CONSIDERATIONS

N/A

5.4 SCREEN FAILURES

Research Referral Form: This will be filled out by PI or qualified designee to assess the appropriateness of TMS in these patients. Patients will be considered ineligible and not screened if they do not meet one or more of the criteria.

Pre-screening Phone Call: All potential participants will undergo a pre-screening phone or a video call to determine whether they meet the inclusion/exclusion criteria. Patients will be considered ineligible if they do not meet one or more of the inclusion/exclusion criteria during pre-screening.

We will collect information on why participants are ineligible or decide not to move forward with the trial.

Screen failures are defined as participants who are considered eligible during the pre-screening phone call, but it was subsequently determined that they do not meet one or more of the inclusion/exclusion criteria. We will collect information on why participants screen fail or decide not to move forward with the trial.

A minimal set of screen failure information is required to ensure transparent reporting of screen failure participants, to meet the Consolidated Standards of Reporting Trials (CONSORT) publishing requirements and to respond to queries from regulatory authorities. Minimal information includes demography, screen failure details, eligibility criteria, and any serious adverse event (SAE).

5.5 STRATEGIES FOR RECRUITMENT AND RETENTION

All subjects will be recruited from the Center for Memory and Aging clinic. An Epic-based list has been created with subjects having either an MCI or early AD diagnosis. Patients and their caregivers will be presented with the option of participating in the study by the PI including providing a brochure at the clinic visits. Participants with clinic visits will meet with research staff. Other patients will be mailed/e-mailed a letter and flyer/brochure. An informed consent form will be provided to those individuals expressing interest in the study. A video or phone encounter will be arranged to provide additional details of the study and informed consent

To reach our target enrollment, we anticipate that we will need to screen 40 people.

Remuneration: Participants will be provided gift cards totaling \$100 per subject. The gift cards will be provided at the end of the study for completing all the study visits.

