7.2 PARTICIPANT DISCONTINUATION/WITHDRAWAL FROM THE STUDY

Participants are free to withdraw from participation in the study at any time upon request.

An investigator may withdraw a participant from the study if:

- Any medical condition, event or situation occurs such that continued participation in the study would not be in the best interest of the subject.
- The participant meets an exclusion criterion (either newly developed or not previously recognized) that precludes further study participation.
- Significant study procedure non-compliance
- Lost-to-follow up; unable to contact subject

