7.3 LOST TO FOLLOW-UP

The reason for participant discontinuation or withdrawal from the study will be recorded on the relevant CRFs. Subjects who sign the informed consent form and undergo only cognitive measures, and not imaging or TMS will not have completed participation and may be replaced.

A participant will be considered lost to follow-up if he or she fails to attend any scheduled study visit and study staff are unable to contact the participant after at least 5 attempts.

The following actions must be taken if a participant fails to attend any required study visit:

- Study staff will attempt to contact the participant, reschedule the missed visit, counsel the participant on the importance of maintaining the assigned visit schedule and ascertain if the participant wishes to and/or should continue in the study.
- Before a participant is deemed lost to follow-up, the investigator or designee will make every effort to regain contact with the participant (where possible, telephone calls or e-mail – if no answer leave a voicemail on the first and last attempt). These contact attempts will be documented.
- Should the participant continue to be unreachable, he or she will be considered to have withdrawn from the study with a primary reason of lost to follow-up.

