8.1.2 BASELINE VISIT (VISIT 2) -WEEK 1 (± 7 DAYS)

- Verify inclusion/exclusion criteria
- Neuropsychological battery as mentioned in Section 8.2.
- This visit is at the clinic (HealthPartners Neuroscience Center [NSC]), is about 2 hours. This may be extended depending on availability of Imaging slot.

- Subject will undergo MRI imaging as mentioned in section 8.2
- Subject will be screened for TMS safety
- Review concomitant medications
- Record any adverse or serious adverse events

8.1.3 TREATMENT VISIT (VISTS 3-5 AND VISITS 6,7) (5 DAYS OVER 2 WEEKS, ± 7 DAYS AFTER VISIT 2)

- Verify inclusion/exclusion criteria
- Motor threshold mapping in Visit 3. Visit 3 will be 5 -7 hours. Visits 4-7 will be 4-6 hours each.
- All visits will be at NSC
- Subject will receive 5 theta burst stimulation sessions at each of the treatment visits
- Visits will be on alternating days (weekdays)
- Review concomitant medications at each visit
- Record any adverse or serious adverse events at each visit

8.1.4 FOLLOW-UP/REPEAT VISIT (VISIT 8)(WEEK 10, 6 WEEKS AFTER VISIT 7 ± 7 DAYS)

- Verify inclusion/exclusion criteria
- Neuropsychological battery as mentioned in Section 8.2.
- This visit is at the clinic (HealthPartners Neuroscience Center [NSC]), is about 2 hours. This may be extended depending on availability of Imaging slot.
- Subject will undergo MRI imaging as mentioned in section 8.2
- Review concomitant medications
- Record any adverse or serious adverse events

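### The full $100 is paid only at the end and only for completing every visit, so a participant who stops TMS has no payment incentive left to attend Visit 8, the only post-treatment assessment

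*Combined protocol and SAP*

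**What the plan says.** Section 5.5 (Strategies for Recruitment and Retention) sets the amount: "Participants will be provided gift cards totaling" $100 per subject. The condition follows: "The gift cards will be provided at the end of the study for completing all the study visits". This is the only incentive in the section, and no other section mentions payment by visit or payment in part. Section 4.3 defines completion in similar terms: "A participant is considered to have completed the study if he or she has completed study visits and assessments".

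The study visits include five TMS visits. Section 8.1.3 says "Subject will receive 5 theta burst stimulation sessions at each of the treatment visits", and on their length: "Visit 3 will be 5 -7 hours. Visits 4-7 will be 4-6 hours each". Section 8.1.4 places the follow-up visit at "WEEK 10, 6 WEEKS AFTER VISIT 7 ± 7 DAYS". The Schedule of Activities (Section 1.3) marks post-treatment MRI, RBANS and GDS at Visit 8 only. Its Early Withdrawal column marks concomitant medications, physical examination and adverse events, and none of the three outcome assessments.

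On missed visits, Section 7.3 says: "Study staff will attempt to contact the participant, reschedule the missed visit". On leaving the study, Section 7.2 says: "Participants are free to withdraw from participation in the study at any time upon request". The replacement provision in Section 7.3 covers only consented subjects who had neither imaging nor TMS.

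**The concern.** The payment is offered as a retention measure, but it works least well where retention is hardest. Someone who gives up TMS partway through, or permanently misses a treatment visit, can no longer satisfy the condition. If that person is to contribute outcome data, he or she must still come back for a visit of about two hours, roughly six weeks after treatment was due to end, with nothing left to earn.

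Two things are at stake. The first is precision: each primary observation needs both scans, the power statement counts all 10 enrolled subjects, and the plan gives no dropout allowance and no missing-data method. The second is selection: if people who tolerate stimulation poorly return less often, the pre/post change describes mainly those who finished all 25 sessions. A single-arm study has no comparator that would reveal this.

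**Working it through.** **1. What the payment rule yields.** Completing all eight visits earns $100. Anything less earns $0 on the text as written, even if Visit 8 is among the visits attended.

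**2. Burden ahead of Visit 8** (Section 8.1.3). Visit 3 takes 5-7 h and Visits 4-7 take 4-6 h each. Minimum: 5 + 4 × 4 = 21 h. Maximum: 7 + 4 × 6 = 31 h. All of it must be completed before Visit 8 can earn anything.

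**3. How often the condition could fail before Visit 8.** The documents give no rate of missed visits. Assume an independent probability q that each TMS visit is missed and never made up. The probability of failing at least one of five is 1 − (1 − q)^5:

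| q (assumed) | Payment lost before Visit 8 | Expected number of 10 |
|---|---|---|
| 1% | 4.9% | 0.5 |
| 2% | 9.6% | 1.0 |
| 5% | 22.6% | 2.3 |
| 10% | 41.0% | 4.1 |

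This shows scale only. It counts people without a remaining incentive, not people who fail to return.

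**4. The plan's own power figure.** Inputs from Section 9.1.2: n = 10, change 0.033, SD 0.033, so d = 0.033/0.033 = 1. The section states no alpha; two-sided 0.05 is assumed from the 95% confidence interval in Section 9.1.1. For a paired (one-sample) t-test, power is P(|T| > t(0.975, n − 1)), with T noncentral t on n − 1 degrees of freedom and noncentrality d√n. With n = 10 the noncentrality is √10 = 3.16 and power is 80.3%, which matches the stated 80%. This treats 0.033 as the SD of the within-person change.

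**5. Power if Visit 8 scans are lost**, same formula:

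| Scan pairs | Power, two-sided | Power, one-sided |
|---|---|---|
| 10 | 80.3% | 89.8% |
| 9 | 74.8% | 86.2% |
| 8 | 68.1% | 81.5% |
| 7 | 60.1% | 75.4% |

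The one-sided column is there because Section 9.1.1 words the test as a difference greater than 0. Only the two-sided version reproduces the stated 80%.

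**6. Selection.** If a fraction m of subjects is lost, the mean among those retained differs from the mean of all by m × (mean change of retained − mean change of lost). As an assumed illustration, if the two groups differ by the plan's own meaningful change of 0.033, losing one of 10 shifts the estimate by 0.1 × 0.033 = 0.0033, and losing two by 0.2 × 0.033 = 0.0066. The documents give no basis for choosing the difference or the fraction.

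**The case against.** The strongest counter-argument is that the plan may lose these scans for a reason unrelated to payment. No section says that a person who stops TMS is asked back for Visit 8. The one case described, a seizure (Section 7.1), leads to early withdrawal procedures, and the Early Withdrawal column has no MRI, RBANS or GDS. Paying for Visit 8 would then pay for a visit the plan does not clearly offer. This stands, and it changes the remedy: the payment edit has to come with a statement about Visit 8 attendance. It does not remove the point, because Section 5.5 would still withhold payment from anyone who did attend.

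It is also fair to say that the documents contain no retention data, that $100 is modest, that unpaid reasons to return remain, and that the power figures describe any lost scan and not this rule in particular. The consent form was not available for this review and may contain a part-payment term. These limits concern the size of the effect, not its direction.

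A reader might infer more than the documents support:

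- That a single missed treatment day forfeits the money. Section 7.3 has staff try to reschedule it, the Schedule of Activities allows ±7 days, and a visit made up still counts.
- That about half the participants may skip sessions, from the 50% headache risk in Section 2.2.3. That is a risk of a self-limiting event, not an attrition rate, and nothing links it to skipped visits.
- That the rule encourages under-reporting of side effects. Payment depends on attendance, not on symptoms, and adverse events are recorded at every treatment visit.
- That Section 5.5 contradicts the freedom to withdraw in Section 7.2. It attaches a cost to stopping but leaves the right intact.

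**Conclusion.** The point holds as a weakness in the retention plan that is cheap to correct. As written, Section 5.5 leaves no payment incentive to attend Visit 8 for anyone who stops TMS or permanently misses a treatment visit, and Visit 8 is the only source of post-treatment data.

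The loss of one scan takes the stated 80% power to about 75%, assuming two-sided alpha 0.05 and 0.033 as the SD of change. On a one-sided reading, power would stay above 80% down to eight pairs. A shift of the estimate toward those who completed all sessions is possible but cannot be sized from the documents. Nor do they show how many participants would fail to return because of the payment rule. The conclusion rests on the protocol text and assumes that the consent form does not already provide part payment. If it does, Section 5.5 needs to be brought into line with it.

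**What to change.** 1. In Section 5.5, keep the $100 maximum and pay by visit attended. Reserve a substantial share for Visit 8, payable regardless of how many TMS visits were completed, and say that stopping TMS does not affect that share.
2. In Sections 7.1 to 7.3, state that participants who stop TMS without withdrawing consent are still asked to attend Visit 8 for MRI, RBANS and GDS. Reconcile this with the Early Withdrawal column of the Schedule of Activities, for example by separating stopping treatment from leaving the study.
3. Match the consent form to both changes.

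The cost is a short protocol and consent amendment, small payouts to participants who do not finish, and slightly more gift-card administration. The maximum payment per participant does not change, and no treatment rule is affected.
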